9.1.2 Adverse Events

An adverse event is defined as any untoward medical occurrence in a clinical trial subject. The event does not necessarily have a causal relationship with study treatment. The investigator is responsible for ensuring that any adverse events observed by the investigator or reported by the subject are recorded in the subject's medical record.

The definition of adverse events includes worsening of a pre-existing medical condition. Worsening indicates that the pre-existing medical condition or underlying disease (eg, diabetes, migraine headaches, gout) has increased in severity, frequency, and/or duration more than would be expected, and/or has an association with a significantly worse outcome than expected. A pre-existing condition that has not worsened more than anticipated (ie, more than usual fluctuation of disease) during the study or involves an intervention such as elective cosmetic surgery or a medical procedure while on study, is not considered an adverse event.

If the severity of an adverse event changes from the date of onset to the date of resolution, record as a single event with the worst severity on the Event eCRF.

For situations when an adverse event or serious adverse event is due to lymphoma report all known signs and symptoms. Death due to disease progression in the absence of signs and symptoms should be reported as the primary tumor type (eg, R/R indolent NHL).

Note: The term “disease progression” should not be used to describe the disease related event or adverse event.

An adverse device effect is any adverse event related to the use of a medical device. Adverse device effects include adverse events resulting from insufficient or inadequate instructions for use, adverse events resulting from any malfunction of the device, or adverse events resulting from use error or from intentional misuse of the device.

The investigator’s clinical judgment is used to determine whether a subject is to be removed from treatment due to an adverse event. In the event a subject, or subject’s legally acceptable representative requests to withdraw from protocol-required therapies or the study due to an adverse event, refer to [Section 8.1](#) for additional instructions on the procedures recommended for safe withdrawal from protocol-required therapies or the study.

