9.2.2.2 Reporting Procedures for Serious Adverse Events

The investigator is responsible for ensuring that all serious adverse events observed by the investigator or reported by the subject that occur after signing of the informed consent through safety follow-up are recorded in the subject’s medical record and are submitted to Amgen. In addition, blinatumomab related serious adverse events will be reported during the long term follow-up. All serious adverse events must be submitted to Amgen within 24 hours following the investigator’s knowledge of the event via the Event CRF.

If the electronic data capture (EDC) system is unavailable to the site staff to report the serious adverse event, the information is to be reported to Amgen via an electronic Serious Adverse Event Contingency Report Form within 24 hours of the investigator's knowledge of the event. See [Appendix B](#) for a sample of the Serious Adverse Event Worksheet /electronic Serious Adverse Event Contingency Report Form. For EDC studies where the first notification of a Serious Adverse Event is reported to Amgen via the eSerious Adverse Event Contingency Report Form, the data must be entered into the EDC system when the system is again available.

The investigator must assess whether the serious adverse event is possibly related to blinatumomab and/or other protocol-required therapies. This relationship is indicated by a "yes" or "no" response to the question: Is there a reasonable possibility that the event may have been caused by the IP?

The investigator is expected to follow reported serious adverse events until stabilization or reversibility.

New information relating to a previously reported serious adverse event must be submitted to Amgen. All new information for serious adverse events must be sent to Amgen within 24 hours following knowledge of the new information. If specifically requested, the investigator may need to provide additional follow-up information, such as discharge summaries, medical records, or extracts from the medical records.

Information provided about the serious adverse event must be consistent with that recorded on the Event CRF.

If a subject is permanently withdrawn from protocol-required therapies because of a serious adverse event, this information must be submitted to Amgen.

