10.5.4 Safety Endpoints

10.5.4.1 Adverse Events

The Medical Dictionary for Regulatory Activities will be used to code all adverse events (AE) to a system organ class and a preferred term. AEs of interest (EOI) categories will be based on search strategies defined by Medical Coding. All adverse event tables will be summarized by treatment group. Treatment-emergent adverse events are events with an onset after the administration of the first dose of protocol-specified therapy.

The subject incidence of AEs will be summarized for all treatment-emergent AEs, serious AEs, AEs leading to withdrawal of protocol-specified therapy, and fatal AEs.

Subject incidence of all treatment-emergent AEs, serious AEs, AEs leading to withdrawal of IP, and fatal AEs will be tabulated by system organ class and preferred term in descending order of frequency; similar summaries will be repeated for EOIs.

Approved

Time to onset and duration of selected EOs (infection and neurologic events) may also be summarized.

For phase 3, a summary of treatment-emergent AEs with at least a 5% higher subject incidence in 1 treatment arm compared to the other will be presented by preferred term. This summary will be repeated for serious AEs using a 10% threshold.

A summary of treatment-emergent AEs will be tabulated by system organ class, preferred term, and worst grade.

Subgroup analyses (if there is a medical or regulatory rationale) will be presented by system organ class and preferred term in descending order of frequency. All races (if appropriate) with less than 5% of the total subjects will be pooled together for summary purposes.

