For the first cycle, the planned cumulative dose will be $(9 \mu\text{g} \times 7 \text{ days}) + (28 \mu\text{g} \times 7 \text{ days}) + (112 \mu\text{g} \times 42 \text{ days}) = 4963 \mu\text{g}$. For 2nd cycles, the planned cumulative dose will be $(9 \mu\text{g} \times 7 \text{ days}) + (28 \mu\text{g} \times 7 \text{ days}) + (112 \mu\text{g} \times 14 \text{ days}) = 1827 \mu\text{g}$. For the entire study, the percent of intended dose of blinatumomab will be the sum of the cumulative doses

across cycles divided by the sum of the planned cumulative doses across the cycles started.

Prior Salvage Regimens

Prior salvage regimens are those medications recorded on the prior anti-cancer therapies CRF where the line of therapy field indicates 1st salvage chemotherapy.

Relative Treatment Duration of Blinatumomab

For 1st cycle, the relative treatment duration will be duration of blinatumomab infusion for that cycle divided by 56 days, the planned duration of infusion. For 2nd cycle (if administered), planned duration of infusion will be 28 days.

Study Day

Study Day 1 is defined as:

The day of the first cycle of blinatumomab.

And Study Day is defined as:

Pre study day 1: study day= (date – date of study day 1)

On and after study day 1: study day= (date - date of study day 1) + 1

Study-level End of Study Date:

The final analysis will occur when all subjects in phase 2 complete long term follow-up.

Subject-level End of Study (EOS) Date

End of study for each subject is defined as the date the subject last completed a protocol-specified procedure. The date will be recorded on the End of Study CRF page.

Treatment-emergent Adverse Event (TEAE)

Treatment emergent adverse event refers to an adverse event that starts after the first dose of blinatumomab up to and including 30 days after the end of blinatumomab. It is indicated by a flag whether an event started before first dose of blinatumomab on the Event CRF page. This reporting window also applies to treatment-emergent serious adverse events (SAEs).

Treatment-emergent Disease-related Event

Treatment emergent disease-related event refers to a disease-related event that starts on or after the first dose of blinatumomab up to and including 30 days after the end of

blinatumomab. It is indicated by a flag whether an event started before first dose of blinatumomab on the Event CRF page. This reporting window also applies to treatment-emergent serious disease-related events (SDREs).

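### Treatment-emergent events are defined by onset alone, so a screening serious adverse event that worsens or proves fatal on blinatumomab may be missing from the incidence tables

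*SAP*

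**What the plan says.** **Definition.** SAP section 6.1: "Treatment emergent adverse event refers to an adverse event that starts after the first dose of blinatumomab". The window closes 30 days after treatment ends. The same section says how the status is set: "It is indicated by a flag whether an event started before first dose of blinatumomab on the Event CRF page". The window is applied to serious events as well. Protocol section 10.5.4.1 takes the same approach: "Treatment-emergent adverse events are events with an onset after the administration of the first dose of protocol-specified therapy". Neither document mentions an event that began before the first dose and worsened after it.

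**Collection.** Protocol section 9.2.2.2 requires reporting of serious adverse events "that occur after signing of the informed consent through safety follow-up". Under protocol section 9.2.2.1, non-serious events are collected only from the first dose.

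**Recording.** Protocol section 9.1.2 covers an event whose severity changes while it is open; the site is to "record as a single event with the worst severity on the Event eCRF". The same section also treats a prior condition that worsens beyond expectation as an adverse event.

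**Reporting.** The subject-incidence tables in SAP section 10.6.1 (all, serious, grade 3 and above, withdrawal, interruption, fatal, treatment-related) are of treatment-emergent events. The listings of serious events, fatal events and deaths carry no such restriction.

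**The concern.** The single-record rule stores the worst grade of an event, whenever that grade was reached. The treatment-emergent rule then keeps or discards the whole record according to its start. For an event that straddles the first dose, the two rules work against each other: the on-treatment grade is captured and then excluded because the event began earlier.

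The case is realistic. Subjects enter after platinum-based salvage chemotherapy, and an infection that qualifies as serious during screening could still be open when the infusion starts. Infection is also one of the selected events of interest in SAP section 10.6.1, and those summaries are restricted to treatment-emergent events too.

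At stake is the safety endpoint in SAP section 4.1.3, the incidence and severity of adverse events. Any error here goes one way, towards understatement. It could also leave outputs that do not reconcile. An event that ended or interrupted treatment would be counted among reasons for discontinuation (SAP section 10.2) or dose modification (SAP section 10.6.7), yet be absent from the corresponding adverse event tables.

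**Working it through.** The plan states no figure on this point, so there is none to reproduce. The check is to follow one case through the rules and then scale it.

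**Case.** A serious infection starts in screening, is open at first dose, worsens on blinatumomab and may end in death.

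1. *Is it on the Event CRF before dosing?* Yes. Serious events are reported from consent (protocol section 9.2.2.2), and screening lasts up to 28 days (protocol section 7.2.1).
2. *Does worsening create a new record?* Not under the severity-change rule. If severity "changes from the date of onset to the date of resolution, record as a single event with the worst severity on the Event eCRF" is the whole instruction. The sample form in protocol Appendix B has one start date and one pre-dose tick box per event. That the record keeps its pre-dose start is an inference from these two facts; the protocol does not state it.
3. *Is it treatment-emergent?* Not on that record. The start precedes the first dose and the flag says so (SAP section 6.1; protocol section 10.5.4.1 gives the same answer).
4. *Which outputs show it?* None of the treatment-emergent tables in SAP section 10.6.1. The listings of serious events, fatal events and deaths do, and a death also counts in overall survival (SAP section 6.2).

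**What else could be affected?**

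| Type of event | Collected from | Can a pre-dose record exist? |
|---|---|---|
| Serious adverse event | Consent (protocol 9.2.2.2) | Yes |
| Non-serious adverse event | First dose (protocol 9.2.2.1) | Not normally |
| Disease-related event | After first dose (protocol 9.2.1) | Not normally |

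The gap is confined to serious events that open in screening and are still open at first dose.

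**Scale.** Take the 36 subjects of SAP section 3.2 and assume that all are treated, so that the Safety Analysis Set is 36. The largest effect of one omitted subject on one incidence is 1/36 = 0.0278, or 2.8 percentage points. Fatal events show the effect most clearly, because counts are likely to be low. With exact (Clopper-Pearson) 95% intervals:

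| Fatal treatment-emergent events | Rate | 95% interval |
|---|---|---|
| 0/36 | 0% | 0 to 9.7% |
| 1/36 | 2.8% | 0.07 to 14.5% |
| 2/36 | 5.6% | 0.7 to 18.7% |

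The tables count subjects, not events. An overall serious or grade 3 and above rate therefore changes only if the subject has no other event that qualifies.

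**The case against.** The strongest objection is that protocol section 9.1.2 already offers a way out. It makes the worsening of a prior condition an adverse event in its own right, and protocol section 7.3.3 collects medical history, including concurrent conditions, up to the first dose. An infection open at first dose fits that description. Its worsening could be entered as a new event with a post-dose start, which is treatment-emergent under both definitions. The eCRF completion guidelines named in protocol section 7.2 might also say how to split such an event, and they are not among the documents. This stands in part. A reader might infer that a worsened screening event is certain to be in no treatment-emergent table, and the text does not support that much. But nothing tells a site to use this route for a serious event already on the Event CRF, and the severity-change rule is the more specific instruction. Two sites could record the same case differently.

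A reader might also infer that the SAP departs from the protocol. It does not, since protocol section 10.5.4.1 is onset-only as well.

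Three further points stand. Grade 3 and 4 laboratory values are recorded as events in their own right (protocol section 9.2.2.1), so a deteriorating subject may well be counted through another event. Exclusion criterion 212 keeps out some subjects with significant illness at entry. And the cases remain visible in the listings.

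**Conclusion.** The point holds in a limited form. Under the rules as written, a screening serious event still open at first dose that worsens or becomes fatal on blinatumomab may be omitted from the serious, grade 3 and above, fatal, withdrawal and interruption tables. It would then be seen only in listings, unless the site enters the worsening as a new event.

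The size is at most 2.8 percentage points per subject in any one incidence, assuming that 36 are treated, and zero where the subject has another qualifying event. The documents give no basis for a number of such subjects, so no total is offered. Extending the point to disease-related events would add little, because these are recorded only after first dose.

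The conclusion rests on one inference: that a single record keeps its pre-dose start. This is a worthwhile clarification of a descriptive safety analysis. It does not touch the primary endpoint.

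**What to change.** 1. In SAP section 6.1 and protocol section 10.5.4.1 together, define a treatment-emergent adverse event as one that starts, or increases in severity or becomes fatal, after the first dose and within the existing window. Changing the SAP alone would set it against the protocol.
2. In protocol section 9.1.2 or the eCRF completion guidelines, state that an event open before the first dose which worsens afterwards is entered as a new event dated at the worsening, as an exception to the single-record rule. This is needed because one record with one start date and a worst grade does not show when the worsening occurred.
3. If the CRF instructions can no longer be changed, review the pre-dose-flagged serious events that were ongoing at first dose. Fatal cases can be identified from the recorded death date.

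The cost is a sentence or two in each document and one line of site guidance. The downside is that treatment-emergent rates may rise slightly.

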
	Safety follow-up	HSCT	Long-term follow-up	
	Approximately 30 days after last dose of blinatumomab or the last day of the last cycle of IC chemotherapy	Within 14 days prior to conditioning regimen	≤ 2 years after EOT: Every 3 months (± 14 days) ^a	> 2 years after EOT: Every 6 months (± 28 days) ^b
General Assessments				
ECOG Performance Status	X			
Medical history and prior therapies	← Continuous from start of treatment →			
Vital signs	X			
Weight	X			
Physical examination	X			
Neurological exam	X			
Clinical tumor assessment	X	X	X	
Serious adverse events	X		X ^c	
Disease related events	X			
Concomitant medications	X		Lymphoma treatment only	
Subject-reported clinical outcome assessment ^d	X			
HSCT Summary ^e			X ^f	
Local Laboratory Assessments				
Hematology	X			
Chemistry	X			
Coagulation	X			
Immunoglobulins	X			
LDH	X	X	X	
Central Laboratory Assessments				
Bone Marrow ^g		per institutional standard		
Pathology tumor block or slides ^h		Collect if lymphoma relapse		
Plasma sample ⁱ		X	X	
Anti-blinatumomab antibodies	X ^j			
Radiographic Assessments				
PET/CT ^k		per institutional standard		

Footnotes defined on the next page.

Approved

CT=computed tomography; CT-DNA=circulating tumor DNA; ECOG=Eastern Cooperative Oncology Group; EOT=end of treatment; IC=investigator's choice; LDH=; PET=positron emission tomography;

^a To occur in person every 3 months (calculated from safety follow up) until completion of a 2-year period after treatment

^b To occur in person or by telephone call every 6 months (\pm 28 days) until study completion

^c Only adverse events possibly related to blinatumomab will be collected

^d Phase 3 only

^e HSCT summary will include completion of details about mobilization, engraftment, specific toxicities, infectious complications

^f HSCT summary is at first post HSCT visit

^g Bone marrow biopsy is not required if PET scan is negative and if not otherwise clinically necessary by investigator discretion

ⁱ At the time of relapse

^j Plasma must be collected, processed, and frozen within 4 hours of phlebotomy

^k For subjects previously randomized to blinatumomab only

^l Based on any scans performed, response is to be assessed locally according to institutional standard and according to the Lugano classification. Any radiographic indication of progression should be followed-up by biopsy.

Approved

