9.2.2 Adverse Events

9.2.2.1 Reporting Procedures for Adverse Events That Do Not Meet Serious Criteria

The investigator is responsible for ensuring that all adverse events observed by the investigator or reported by the subject that occur from the first dose of IP through the safety follow-up visit are reported using the Event CRF. Adverse events considered by the investigator to be possibly related to blinatumomab will be reported from the beginning of transplant conditioning during the long-term follow up until completion of a 2-year period after treatment.

Approved

The investigator must assign the following adverse event attributes:

- Adverse event diagnosis or syndrome(s), if known (if not known, signs or symptoms),
- Dates of onset and resolution (if resolved),
- Severity [and/or toxicity per protocol],
- Assessment of relatedness to blinatumomab or protocol required medication or medical device, and
- Action taken.

The adverse event grading scale used will be the CTCAE. The grading scale used in this study is described in [Appendix A](#).

The investigator must assess whether the adverse event is possibly related to blinatumomab. This relationship is indicated by a “yes” or “no” response to the question: Is there a reasonable possibility that the event may have been caused by the investigational medicinal product?

The investigator must assess whether the adverse event is possibly related to any study-mandated activity (eg, protocol-required therapies). This relationship is indicated by a “yes” or “no” response to the question: “Is there a reasonable possibility that the event may have been caused by a study activity (eg, protocol-required therapies), and/or procedure”?

The investigator is responsible for reviewing laboratory test results and determining whether an abnormal value in an individual study subject represents a change from the subject’s baseline values. All grade 3 and grade 4 laboratory values should be recorded as adverse events. In addition, if signs or symptoms are associated with a laboratory abnormality, the signs/symptoms and the laboratory abnormality should all be recorded as adverse events. The laboratory abnormality and any signs/symptoms should be graded according to their own CTCAE criteria.

The Investigator is expected to follow reported adverse events until stabilization or reversibility.

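### The SAP's undeclared 30-day limit on treatment-emergent events keeps later blinatumomab-related events out of every incidence table

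*SAP*

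**What the plan says.** **SAP.** Section 6.1 closes the treatment-emergent window "up to and including 30 days after the end of blinatumomab" and applies the same limit to serious events and to disease-related events. Section 10.6.1 then builds its incidence tables (all, serious, grade 3 and above, fatal, treatment-related and so on) from treatment-emergent events. The summaries of events of interest, disease-related events and subgroups are restricted in the same way. Only the subject listings of serious events, fatal events and deaths carry no stated time limit. Section 11, on changes from the protocol, covers only who reads the scans and whether clinical assessment is used for the response, duration, PFS and transplant endpoints.

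**Protocol, definition.** Section 10.5.4.1: "Treatment-emergent adverse events are events with an onset after the administration of the first dose of protocol-specified therapy". It gives no end date.

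**Protocol, collection.**
- Section 9.2.2.1: all adverse events "that occur from the first dose of IP through the safety follow-up visit are reported using the Event CRF". Those that the investigator attributes to the study drug "will be reported from the beginning of transplant conditioning during the long-term follow up until completion of a 2-year period after treatment".
- Section 9.2.2.2: in addition, "blinatumomab related serious adverse events will be reported during the long term follow-up".
- Table 9 in section 7.1 marks long-term follow-up on the serious adverse event row, with the footnote "Only adverse events possibly related to blinatumomab will be collected".
- Section 7.2.4 puts the safety follow-up visit at about 30 (±3) days after the last dose. It allows a later visit when a planned cycle is delayed beyond 30 days, and requires the visit before any conditioning regimen or new anti-lymphoma treatment.

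**The concern.** The protocol asks sites to report late events that the investigator attributes to blinatumomab, but the SAP plans no summary of them. A reader of the treatment-related tables would take them to cover what was collected, when they stop 30 days after the last dose. The narrower definition is also not disclosed where the SAP lists its departures from the protocol. Evaluating safety is a secondary objective in both documents, so the study report should show how related events were counted and where the late ones went.

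**Working it through.** No stated figure needs to be reproduced. The check is a comparison of text plus day arithmetic. Days are counted from the last infusion (day 0) unless stated.

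**1. Definition.** Protocol 10.5.4.1: onset after first dose, open-ended. SAP 6.1: onset after first dose, closed at day 30. SAP Section 11 is silent. The two differ, and the difference is undeclared.

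**2. All-cause events around the safety visit.** Let *v* be the day of the visit. Days collected but outside the SAP window = max(0, *v* − 30).
- *v* = 27: 0 days. Here the SAP window runs 30 − 27 = 3 days beyond all-cause collection.
- *v* = 30: 0 days.
- *v* = 31: 1 day. *v* = 33: 3 days.
- Delayed visit: with no interruption, Cycle 1 infusion ends on study day 56 and the cycle on study day 70. Optional Cycle 2 may start 2 to 4 weeks later (protocol section 3.1), which is 14 + 14 = 28 to 14 + 28 = 42 days after the last infusion. If Cycle 2 is planned for the latest date but not given, and the visit takes place then, 42 − 30 = 12 days fall outside. Section 7.2.4 states no upper limit. If Cycle 2 is given, the SAP window runs from the end of that cycle and nothing is lost in the gap.

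**3. Related events after transplant conditioning.** Take a subject given Cycle 1 only, without interruption.
- SAP window closes at study day 56 + 30 = 86.
- PET/CT is at about study day 70. Section 7.2.6 records whether conditioning began within 30 days of that assessment, so take study days 70 to 70 + 30 = 100 as the illustrative range. This is an assumption; conditioning may be later.
- Conditioning at study day 70: the SAP window covers the first 86 − 70 = 16 days of the related-event period. Conditioning after study day 86: it covers none.
- Taking 2 years as 730 days from the last infusion, the related-event period starts at day 70 − 56 = 14 and lasts 730 − 14 = 716 days. At best, 16/716 = 2.2% of it lies inside the window. This is calendar time, not a share of events.

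**4. Where a late related event would appear.**

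| Event, onset after day 30 | Incidence table | Listing |
|---|---|---|
| Related, serious or fatal | none | serious, fatal or deaths listing |
| Related, non-serious | none | none planned |
| Other cause, non-serious, collected because the visit was after day 30 | none | none planned |

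**5. Effect of one subject.** With the planned 36 subjects, one subject left out changes an incidence by 1/36 = 2.8 percentage points.

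**The case against.** The best defence is that the SAP specifies something the protocol left open. All-cause collection stops at a visit set nominally at 30 days, so a 30-day window fits the design and is not wrong in itself. That stands, and it is why the window need not be changed. It does not explain why Section 11 omits the limit, or why related events collected after it have no summary.

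Three stronger readings are tempting, and the documents do not support them.
- *Every on-time safety visit loses up to 3 days.* Visits on days 27 to 30 are on time and lose nothing. Subjects going to transplant or new treatment are seen beforehand, sometimes earlier still. For early visits the SAP window is wider than all-cause collection.
- *Two years of non-serious related events are lost for every subject.* Collection of late non-serious related events rests on one sentence in section 9.2.2.1, which starts at transplant conditioning. Read literally, it does not reach subjects who are never transplanted. Section 9.2.2.2 and the marked row in Table 9 concern serious events.
- *Late serious toxicity disappears.* The listings of serious events, fatal events and deaths are not stated to be limited to 30 days, so these events remain visible, though uncounted.

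It is also fair to say that this SAP covers a single-arm analysis. No between-arm safety comparison can be biased, and the primary endpoint is untouched.

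**Conclusion.** The point holds as a minor reporting and documentation defect. The SAP narrows the protocol's definition without declaring it. As a result, blinatumomab-related events with onset more than 30 days after the last dose enter no incidence table, and the non-serious ones reach no planned output. All-cause events are affected only when the safety visit falls on days 31-33 or is delayed.

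The size in events is unknown, because the documents give no rate for late related events. A reader might infer from the calendar share in the working that most related toxicity is under-reported. That does not follow: days outside the window are not events, and nothing in the documents shows how many would occur there.

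The conclusion assumes that the listings are not restricted to treatment-emergent events (the SAP does not say that they are), and that section 9.2.2.1 is followed as written.

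**What to change.** 1. Keep the 30-day window for the main treatment-emergent tables and declare it in SAP Section 11 as a departure from protocol section 10.5.4.1.
2. Add one separate table, by seriousness and grade, of blinatumomab-related adverse events and serious adverse events with onset more than 30 days after the last dose. A footnote should say that non-serious related events in this period are collected only from the start of transplant conditioning.
3. Add one listing of any other adverse event collected up to the safety follow-up visit but with onset after day 30.

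Do not replace 30 days with a fixed 33. For subjects seen early, that would run further past the end of all-cause collection and make ascertainment uneven. Do not merge the late events into the main tables either, since that would mix a period in which all events are collected with one in which only related events are.

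The cost is one SAP sentence, one table and one listing, with no new data.
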